Appendix 1 – DCT Evaluation Framework

Below is shown the Evaluation Framework for the NHS Test Trace Programme of Evaluation of Daily Contact Testing. Individual pilots or studies run within this programme address a subset of these dimensions / questions.

- Operational Feasibility
 - How acceptable is the testing regime to those being tested?
 - \circ What operational burden does it place on the host institution?
 - What are the implications for scaling up?
- Scientific Knowledge
 - What is the operational performance of the testing technology in this setting? Do we see concordance between new technologies and dual swab PCRs?
 - Are the assumptions used in previous modelling of the effectiveness of new testing technologies born out in real-world practice?
- Public Health Effectiveness
 - What is the uptake of testing? How does that vary by socio-demographic factors?
 - What effect does testing have on the spread of infection within the bubble / host institution? Does it increase or decrease compared to self-isolation? Could any modifications to the testing intervention improve its effectiveness?
- Behavioural Factors
 - \circ Why do people choose or decline to take part in testing?
 - What factors affect whether people complete the regime of tests as intended?
 - How do people respond to positive and negative test results? How do they alter their behaviour?
- Broader Social/Economic Benefit
 - What impact does this have on people's daily activities (for example being at work or school)?

Appendix 2 – Self-Reported Behaviours Survey Instrument

1. Recent activities

- a. Thinking about yesterday, please tick all the things you did:
 - a. Went to school
 - b. Went out to go to a shop, cafe or any other place outside my home (not school)
 - c. Spent time outdoors (not at school) with people I do not live with (for example, in the park, playing, walking)
 - d. Spent time indoors (not at school or online) with friends or family I do not live with
 - e. Went out for any other reason (please say what this was for)
 - f. None of these

If you went to school yesterday please answer this question:

How often did you do the following? [responses = Much less than usual, Less than usual About the same as usual More than usual, Much more than usual]

Wore a face covering Spent time with people in my bubble Spent time with people not in my bubble Washed my hands

- b. Thinking about the last 7 days, please say how often you have done each of these things: [options = never, once or twice, a few times, most days)
 - a. Went to school
 - b. Went out to go to a shop, cafe or any other place outside my home (not school)
 - c. Spent time outdoors (not at school) with people I do not live with (for example, in the park, playing, walking)
 - d. Spent time indoors (not at school or online) with friends or family I do not live with
 - e. Went out for any other reason (please say what this was for)
 - f. None of these
- c. Comparing the last 7 days with the week before that did you have more or less close contact with people you do not live with (indoors and for more than 15 minutes) last week?
 - Much more contact
 - Slightly more contact
 - About the same
 - Slightly less contact
 - Much less contact

2. Test result

a. During the past week, have you had any tests for coronavirus? YES / NO

[If Yes]

Did you have a positive test result for any test? (This means that the test showed you did have COVID.)

YES/NO

[If Yes]

When did you test positive?

[Responses: Today, yesterday, 2-3 days ago, 4-5 days ago, 6-7 days ago]

Next question for those in DCT group only

- b. How confident are you that your test results were accurate?
 - Completely confident
 - Very confident
 - Fairly confident
 - Not very confident
 - Not at all confident

3. Preferences for testing

If you have been in contact with someone testing positive for coronavirus the usual option is to self-isolate by staying at home for 10 days.

A new option is to carry out daily tests for up to 7 days, which means that every day you have a negative test you can carry on with your normal activities and do not need to self-isolate.

Which option do you prefer?

- Strongly prefer 10 day self-isolation option
- Somewhat prefer 10 day self-isolation option
- No preference for either option
- Somewhat prefer daily testing option
- Strongly prefer daily testing option

4. Demographics

What school do you attend?

How old are you?

What is your gender?

- Male
- Female
- Prefer to self-describe
- Prefer not to say

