2.1 Study Hypotheses and Objectives

The study hypotheses are as follows:

- 1. That the intervention arm (daily contact testing) will have increased school attendance compared to the control arm (self-isolation) (i.e. superiority)
- 2. That the level of transmission of COVID-19 in the schools in the intervention arm (daily contact testing) is not inferior to (i.e. not higher than in) the control arm (self-isolation)

The primary objective of the study is to assess the effectiveness, in terms of in-school COVID-19 transmission and student / staff in-school days lost to self-isolation, of two different COVID-19 control strategies implemented at a school level using regular active case finding with lateral flow antigen tests.

Both arms of the study will include weekly active case finding of students and biweekly active case finding of staff. The arms will differ in the management of contacts of positive cases:

- (i) Arm 1: routine self-isolation of all first-order contacts of positive tests
- (ii) Arm 2: daily LFD testing of asymptomatic first-order contacts of positive tests at the beginning of the school day with self-isolation restricted to individuals with positive results.

Co-Primary End-Points

- (i) Number of school days lost from COVID-19 or contact with COVID-19 cases
- (ii) Estimated number and rate of within-school COVID-19 transmission events

Secondary End-Points

- (iii) Number and rate of positive contacts missed by daily LFD testing
- (iv) Number and rate of COVID-19 cases transmitted to the school-based and household firstorder contacts of the index case ("primary attack rate")
- (v) Number and rate of COVID-19 cases transmitted to the school-based and household second-order contacts of the index case ("secondary attack rate")
- (vi) Number and proportion of school attendees testing COVID-19 positive in weekly active case finding
- (vii) Proportion of student and staff first-order contacts who accept an offer of daily contact testing with LFD devices

Secondary objectives:

- 1. To gain knowledge on the operational aspects of this process; specifically, to understand uptake and barriers for schools and individuals as well as operational challenges.
- 2. To improve understanding of a range of behavioural factors, including reasons for participating, response to negative and positive test results, and compliance with self-isolation

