3.8 Assessment of Behavioural and Other Outcomes

Assessment of the behavioural components of the evaluation framework will include the following:

- 1. Survey of a) self-reported out of school activities and contacts (for comparison in testnegative, test-positive and self-isolating participants); b) views of testing (compared with selfisolation)
- 2. PPI input and qualitative research to understand views and experiences of and responses to testing of pupils, parents and school staff teachers and others

Participants in both the Interventional and Control Arms will be invited to complete a very brief online survey; this will include all participants who are a first-order contact of a positive index case. Measurement will be on day 7 after notification of being the contact⁷, using self-report measures of social contacts and other behaviours adapted from measures already in use. To promote honest self-reporting, an anonymous survey instrument will be used (as in the previous 'Agile Lighthouse' evaluation of DCT), which can be found in Appendix 2.

Outcome 2 focuses on gathering the perceptions, experiences and beliefs of those involved in the testing process, including pupils, parents, teachers and administrators. In collecting this data, it is crucial that the burden on teachers and school staff is reduced as far as possible during what is already an extremely challenging time for them. We have explored the potential for using existing research vehicles (e.g. the Pupil and Parent Panel omnibus survey), but these would not allow us to deliver the objectives of the present study. The bespoke data collections have therefore been streamlined to lower burden. The approaches that will be used are:

- User research carried out in two waves within both Phase 1 and Phase 2:
 - Wave 1: At the beginning of the testing period to explore the practicalities of delivering the protocol within the 'intervention arm' schools. This will be no more than ten interviews (anticipated approx. 20-30 minutes, no more than 1 participant per school site) with school staff (teachers and non-teachers) involved in management/implementation focusing on the process and expectations for the testing. Data will enable a view of the study implementation (allowing adjustments to be made if required) as well as the feasibility of wider rollout.

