4.2.1 Interventional (Daily Contact Testing) Arm

All those in the same first-order close contact group as the positive case will be offered the option of being tested by LFD at the start of every school day, until day 7 after being notified of being a contact¹¹. Those who do not consent to daily testing will be subject to the process outlined in Section 4.4. LFD antigen testing will be via one of two delivery models:

- 1. Supervised anterior nares swabbing, with device use assisted within a school's ATS model. The workforce for this will be trained according to national NHS T&T standard process.
- 2. Once a suitable protocol is available, at-home self-anterior nares self-swabbing under supervision of the parent / guardian (in alignment with national NHS T&T guidance). Swab samples will be self-applied at home to the LFD device and the result self-read by students under supervision of the parent / guardian, or by the parent / guardian if the student does not feel confident to use the device themselves.¹²

Those that test **negative** on the LFD negative at the start of the school day will be allowed to attend school for that day until their next test is due. It will not allow them to avoid self-isolation outside the school setting, and this will be communicated to participants using accessible, standardised materials drawing on behaviour change techniques and developed with user feedback to ensure they are credible and motivating. Participants will be required to self-isolate on days where a test has not been performed (e.g. weekends). If a non-tested day occurs at the end of Daily Contact Testing, a further negative test will be required to complete and release from the Daily Contact Testing protocol.

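### The day 7 survey's fixed 7-day recall items blend days before and after a positive test, and its item about the previous day misses in-school behaviour for contacts notified on a Monday or Sunday

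*Protocol*

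**What the plan says.** Section 2.1 lists, under secondary objective 2, understanding of "response to negative and positive test results, and compliance with self-isolation". Section 3.8 serves this with one brief anonymous online survey of first-order contacts in both arms, in which out-of-school activities and contacts are recorded "for comparison in testnegative, test-positive and self-isolating participants". On timing it says "Measurement will be on day 7 after notification of being the contact", with the notification day as day 0.

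The instrument is in Appendix 2. Part 1 has three recall items, none of which branches on test result or weekday:

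- Item a: "Thinking about yesterday, please tick all the things you did". A block on in-school behaviour follows, only for those who were in school that day.
- Item b: "Thinking about the last 7 days, please say how often you have done each of these things", answered in four categories from never to most days.
- Item c: "Comparing the last 7 days with the week before that did you have more or less close contact" with people outside the household.

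Part 2 then asks whether any test was positive and, if so, when, in bands: "Responses: Today, yesterday, 2-3 days ago, 4-5 days ago, 6-7 days ago".

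**The concern.** A contact in DCT may attend school on days with a negative lateral flow test and must stop attending after a positive one. Item b collects one answer over a window that usually contains both periods, so what is reported for a test-positive contact is not behaviour after a positive result. Item c has the same window. Knowing the date of the positive does not help, because a category such as once or twice cannot be divided at that date.

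Separately, day 7 falls on the same weekday as notification. For some contacts the previous day is therefore a weekend day without a lateral flow test or school, and the in-school block yields nothing. This information is lost when the form is completed, and no later analysis can recover it.

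**Working it through.** The protocol gives no figure on this point, so there is none to reproduce. The check is a count of days.

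**Inputs.** Day 0 is notification and the survey is on day 7 (Section 3.8). DCT tests run on school days from day 1 to day 7 (Section 4.2 note on timings; Section 4.2.1), with none on non-school days (Section 3.1). The distribution of the day of first positive, d, is not given for DCT contacts and is assumed below. The last 7 days can be read as days 1–7 or days 0–6.

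**Share of the window before the result.** This is (d − 1)/7 for days 1–7 and d/7 for days 0–6.

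| Day of positive d | 1 | 2 | 3 | 4 | 5 | 6 | 7 |
|---|---|---|---|---|---|---|---|
| Survey timing band | 6–7 days | 4–5 days | 4–5 days | 2–3 days | 2–3 days | yesterday | today |
| Item b, days 1–7 | 0% | 14% | 29% | 43% | 57% | 71% | 86% |
| Item b, days 0–6 | 14% | 29% | 43% | 57% | 71% | 86% | 100% |
| Item a (day 6) | after | after | after | after | after | same day | before |

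**Averages over assumed distributions.** Front-loaded means that the weight falls by a factor of 0.7 per day; back-loaded is the reverse. School-day figures average over notification from Monday to Friday. Each cell for item b gives the days 1–7 reading, then days 0–6.

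| Assumption | Item b pre-result, all days | Item b pre-result, school days only | Item a wholly after result, all days / school days |
|---|---|---|---|
| Even | 43%, 57% | 46%, 60% | 71% / 64% |
| Front-loaded | 24%, 39% | 26%, 41% | 91% / 87% |
| Back-loaded | 61%, 76% | 65%, 79% | 44% / 35% |

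Item b therefore ranges from about 24% to 79% pre-result. Item a lies wholly after the result for 35% to 91% of positives.

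**Can the timing question rescue item b?** Only by keeping the oldest band, 6–7 days ago, which on day 7 means day 1 or day 0. Since DCT testing starts on day 1, only day-1 positives remain: 1/7 = 14% under an even spread over all days. With school-day testing it is 1/5 for Monday to Thursday notification and none for Friday, whose day 1 is a Saturday, giving (4 × 1/5 + 0)/5 = 16%. The base is small: Section 3.9 expects about 2 positives per index case (5% of 35 = 1.75).

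**Weekday of item a.** Notification on Monday gives a survey on Monday about Sunday; notification on Sunday gives a survey on Sunday about Saturday. All other notification days give a weekday. The weekend share is 1/5 = 20% if notifications are even over Monday to Friday, and 2/7 = 29% if even over seven days. Any 7-day window holds five weekdays and two weekend days, so weekday does not distort item b.

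**The case against.** The best defence has four parts.

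1. *The comparison concerns out-of-school activities, and the rule for those does not change at a positive result.* Sections 3.1 and 4.2.1 tell DCT contacts to self-isolate outside school even after a negative test. This stands. A reader might infer that permitted behaviour is being counted as behaviour after the result, so that adherence after a positive looks worse than it is. The protocol supports that only for the answer on going to school. For shops, outings and mixing, the blend is of behaviour to be avoided on both sides of the result, and the direction of bias is unknown.

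2. *Item a already supplies post-result data.* This also stands, for positives on days 1 to 5, and the timing bands allow those respondents to be selected. The blending belongs to items b and c. But item a covers one day only.

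3. *The weekend problem is narrow.* Outside school, contacts are to isolate on weekdays and weekends alike, so item a remains usable for out-of-school activities. What is lost is that day's attendance answer and the in-school block. A reader might take the Monday example in Section 4.2 to mean that all contacts in a Monday-testing school are affected, but index cases also arise from symptomatic and non-school testing.

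4. *A common fixed window is a reasonable choice for a short survey.* It is. Replacing it for positives with recall since the positive would give windows of unequal length, and the frequency categories would no longer mean the same thing. This argues for adding an item and against replacing item b.

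None of this makes item b divisible at the result date. The qualitative interviews explore reactions to a positive result but are not designed to be generalisable (Appendix 7).

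**Conclusion.** The point holds as a limit on what two survey items can show. For contacts whose first positive comes after day 1 of DCT, items b and c blend days before and after the result, and the response to a positive result cannot be estimated from item b. That follows from the fixed window, the coarse categories and the anonymity, which rules out linkage to test records.

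The size is uncertain. A reader might infer that about half the window precedes the result, but that needs an even spread of positives, which the protocol does not state. The assumptions tried here give roughly a quarter to four fifths.

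The second part holds for contacts notified on a Monday or Sunday: 20% to 29% of respondents under the two even-notification assumptions, who give no in-school behaviour data.

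A behavioural secondary objective is affected and no co-primary endpoint is, so this ranks as a minor improvement worth making before the form is used.

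**What to change.** - Keep items a and b as they are, as a common window for all respondents.
- After the timing question in part 2, add one conditional tick-list for those reporting a positive result: *since the day you tested positive, have you done any of these?* Use the activities already listed.
- Ask the in-school behaviour block about *the last day you were in school during your daily testing*.
- Record the survey date, so that item a can be stratified by weekday.
- For the test-positive comparison, state that it uses item a limited to positives two or more days earlier, together with the new tick-list, and does not use item b.

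The cost is one extra item for a few respondents. Recall for the school block is up to about 3 days for contacts still testing negative (a Monday survey about Friday). It is longer for those who tested positive early: a day-2 positive last in school on day 1 would be recalling 7 − 1 = 6 days. The tick-list still covers periods of different length, so it should be reported by timing band.

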3.2 Methods

3.1 Overview of Design

This is a pragmatic cluster randomised controlled study. Eligible participating schools will be stratified according to institution type, size, Free School Meal prevalence and local COVID-19 prevalence and randomly allocated into the two study arms. A schematic summarising the study design and participant sub-groups can be found in Figure 2 below.

Regular Active Case Finding. In schools participating in either arm of the study, consent will be obtained from adults/parents/guardians for voluntary weekly testing of all students and biweekly testing of all staff⁵. Tests will be performed with lateral flow devices (LFD)*, and results will be reported in the NHS Test and Trace database. LFD Tests will initially be performed as an assisted test in a school setting. Once a reliable protocol for home testing and recording of LFD is available, schools will be offered the option for at-home self-testing for weekly case finding.

Individuals who test positive will self-isolate and identify first-order contacts according to national guidelines. In addition, symptomatic cases who test positive via NHS Test and Trace, and asymptomatic cases who test positive outside the in-school testing regimen will self-isolate and report their results to the school. All individuals with a positive test will be asked to provide a PCR swab test for genomic sequencing.

1. Intervention (Daily Contact Testing) Arm

a. Public Health Intervention: Consenting first-order contacts of a COVID-positive index case will receive daily contact testing for 7 days from the point of being notified they are a close contact⁶. This will consist of a daily LFD*. Those that receive a negative LFD result can attend school for that day, but other than travelling to and from school will be instructed to continue to self-isolate outside the school setting. Those that receive a positive LFD result should not attend school and will be instructed to self-isolate for 10 days according to national guidelines. The contacts of all first-order contacts (i.e. 'second-order contacts') will be identified to allow the determination of secondary attack rate.

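### Survey item 1c on change in close contact does not exclude school, so it cannot fairly compare out-of-school behaviour between contacts attending under daily testing and contacts who self-isolate

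*Protocol*

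**What the plan says.** Section 3.8 of the Protocol describes the survey as covering "self-reported out of school activities and contacts (for comparison in testnegative, test-positive and self-isolating participants"). It goes to first-order contacts in both arms, and "Measurement will be on day 7 after notification of being the contact". It serves the secondary objective in section 2.1 on responses to test results and compliance with self-isolation.

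In Appendix 2, items 1a (yesterday) and 1b (last 7 days) offer contact options that leave school out. The indoor option reads "Spent time indoors (not at school or online) with friends or family I do not live with" and the outdoor one begins "Spent time outdoors (not at school) with people I do not live with". Item 1c then asks all respondents to compare the last 7 days with the preceding week: "did you have more or less close contact with people you do not live with (indoors and for more than 15 minutes) last week". Its five answers run from much more to much less contact. It carries no school exclusion.

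On what each group may do, section 3.1 says of DCT contacts: "Those that receive a negative LFD result can attend school for that day". Section 4.2.1 adds of the negative result: "It will not allow them to avoid self-isolation outside the school setting". Control-arm contacts (section 3.1) and intervention-arm contacts who decline DCT (section 3.3) self-isolate and so are not in school.

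**The concern.** A lesson is indoor contact of more than 15 minutes with people the pupil does not live with, so it counts under item 1c as worded. Whether a contact is in lessons during the recall week follows largely from the contact policy, not from how that person behaves outside school. The item therefore mixes permitted attendance with the behaviour that the survey is meant to compare.

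The direction of the distortion is predictable: attenders appear to have cut their contact less than isolators. Someone reading the answers as a measure of adherence could take this for relaxed precautions after negative tests, which is one of the questions the behavioural objective addresses.

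**Working it through.** The protocol states no score, effect size or analysis for item 1c, so there is no figure to reproduce. The check compares the wording with the purpose, followed by a simple illustration.

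**Wording against purpose**

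| Element | Source | School excluded? |
|---|---|---|
| Purpose: activities and contacts compared between test-negative, test-positive and self-isolating participants | Section 3.8 | Yes, stated as out of school |
| Outdoor and indoor contact options | Appendix 2, items 1a and 1b | Yes |
| Change in indoor close contact of more than 15 minutes | Appendix 2, item 1c | No |

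Because the survey is taken on day 7 after notification, the 7-day recall window coincides with the DCT or isolation period. This is when attendance differs most between the groups.

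**Illustration** (assumptions, not figures from the protocol)

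- There are 5 school days in each week, each with qualifying indoor contact for anyone attending.
- In the week before notification there were 0 to 2 further contact-days outside school, the same for both groups.
- Both groups comply perfectly outside school in the last 7 days.

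Ratio = contact-days in the last 7 days ÷ contact-days in the week before.

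- Week before, both groups: 5 + 0 = 5 up to 5 + 2 = 7 contact-days.
- DCT attender, last 7 days: 5 + 0 = 5. Ratio 5/5 = 100% down to 5/7 = 71%. Plausible answer: *about the same* or *slightly less*.
- Self-isolator, last 7 days: 0 + 0 = 0. Ratio 0/5 to 0/7 = 0%. Plausible answer: *much less*.

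On the ordered scale, *about the same* is two categories from *much less* and *slightly less* is one. The gap is therefore 1 to 2 categories with identical out-of-school behaviour.

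Fewer attended days, through a missed test or a positive result, shrink the gap. With 3 attended days, for example, the ratio is 3/5 = 60% down to 3/7 = 43%. It stays above the isolator's 0% for anyone who attended at all.

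**With school excluded**

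The attender and the isolator each have 0 qualifying contact-days in the last 7 days, against the same 0 to 2 the week before. Both give the same answer and the artefact disappears.

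**Can the analysis repair it?**

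Item 1b records how often the respondent went to school, so attenders can be identified. It cannot divide a single answer to 1c into school and non-school contact. Stratifying by attendance does not help either, because attendance largely defines the contrast between test-negative and self-isolating contacts.

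**The case against.** The strongest defence is that item 1c was meant to capture total contact. Appendix 2 does ask about conduct in school (face coverings, handwashing, mixing within and outside the bubble), and section 3.8 also speaks more generally of measures of social contacts and other behaviours. Total contact is a legitimate quantity when the question is transmission. On that reading the item is valid, and only its use for an out-of-school comparison would be wrong. But the purpose stated for the group comparison is "self-reported out of school activities and contacts", and total contact can be asked separately.

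Several limits on the point stand:

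- The contact options in items 1a and 1b exclude school and still support a fair out-of-school comparison.
- A reader might take 1c to be the only question on change in contact. It is not: those who went to school yesterday are also asked about time with people in and outside their bubble, relative to usual. Item 1c is the one put to all respondents and the one using the indoor, 15-minute definition.
- A reader might infer that the survey will report DCT attenders as less compliant. The protocol does not name 1c as an adherence measure and states no analysis of it, so the misreading is a risk rather than a planned result. Nor is *about the same* a report of increased contact.
- A reader might score the answers from −2 to +2 and apply the 70% DCT uptake in section 3.9, giving 0.70 × 2 = 1.4 points between arms (0.70 × 1 = 0.7 if attenders answer *slightly less*). The documents do not support such a figure. They give no scoring, section 3.8 compares participants by test and isolation status rather than by arm, and not every volunteer will attend throughout.

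**Conclusion.** The point holds as a wording defect in one survey item. As written, item 1c is liable to show a smaller reduction in contact among contacts attending under DCT than among self-isolators when both comply fully outside school. It cannot serve as a fair comparison of out-of-school behaviour between test-negative and self-isolating participants.

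The size is illustrative: one to two answer categories under the attendance and prior-contact assumptions above, and less with fewer attended days. The direction rests only on the wording of the item and on who may attend school.

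The consequence is confined to a secondary behavioural objective. The co-primary endpoints and the sample size do not depend on this item. It merits correction because the bias is predictable, cannot be removed afterwards and is cheap to prevent.

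**What to change.** Add *(not at school)* to item 1c, in line with the contact options in 1a and 1b. Refer to the last 7 days consistently; the question now opens with that period and closes by calling it last week. If total contact is also wanted, ask it as a separate item and keep it out of the out-of-school adherence comparison.

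The cost is a few words in the instrument before fieldwork. The one possible downside is some loss of comparability, since section 3.8 says the measures were adapted from ones already in use. The documents do not show those sources, so this cannot be sized, but it is likely to be small.
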